12.4.4 Criteria for Defining the Severity of an Adverse Event

The investigator will use the following definitions to rate the severity of each AE:

- Mild: No disruption of normal daily activities
- Moderate: Affects normal daily activities
- Severe: Inability to perform daily activities

12.4.5 Reporting Procedures for Serious Adverse Events

The investigator must complete and submit an SAE worksheet containing all information that is required by local and/or regional regulations to the sponsor by fax or email immediately (within 24 hours of awareness).

The SAE worksheet must be signed by a medically qualified investigator (as identified on delegation of authority log). Signature confirms accuracy and completeness of the SAE data as well as the investigator causality assessment including the explanation for the causality assessment.

If the SAE is associated with emergency unblinding by the investigator as outlined in [Section 6.3.4 Breaking the Treatment Code for Emergency], this is to be recorded on the 11 Feb 2021 Astellas Page 80 of 157

Sponsor: APGD EudraCT number 2016-001767-37

- CONFIDENTIAL -

SAE worksheet. On the SAE worksheet, the investigator is to include when unblinding took place in association with the SAE.

ISN/Protocol: 178-CL-204

For contact details, see [Contact Details of sponsor's Key Personnel]. Fax or email the SAE/special situations worksheet to:

Astellas Pharma Global Development Inc.
US Pharmacovigilance
North America [contact]
North America alternate [contact]
International [contact]
Email: [contact]

If there are any questions, or if clarification is needed regarding the SAE, please contact the sponsor's medical monitor/study physician or their designee [Contact Details of Sponsor's Key Personnel].

Follow-up information for the event should be sent promptly (as soon as available but no longer than within 7 days of the initial notification).

Full details of the SAE should be recorded on the medical records, SAE/special situation worksheet and on the electronic data source.

The following minimum information is required:

- International study number/study number
- Subject number, sex and age
- Date of report
- Description of the SAE (event and seriousness criteria)
- Causal relationship to the IP (including reason)
- Blinded regimen

The sponsor or sponsor's designee will medically evaluate the SAE and determine if the report meets the requirements for expedited reporting based on seriousness, causality, and expectedness of the events (e.g., SUSAR reporting) according to current local/regional regulatory requirements. The sponsor or sponsor's designee will submit expedited safety reports to competent authorities and concerned ethics committee per current local regulations and will inform the investigators of such regulatory reports as required. Investigators must submit safety reports as required by their IRB/IEC within timelines set by regional regulations (e.g., EMA, FDA) where required. Documentation of the submission to and receipt by the IRB/IEC of expedited safety reports should be retained by the study site. In the US, FDA expedited IND reporting guidelines will be followed.

The sponsor will notify all investigators responsible for ongoing clinical studies with the test product of all SUSARs, which require submission per local requirements IRB/IEC.

The investigators should provide written documentation of IRB/IEC notification for each report to the sponsor.

ISN/Protocol: 178-CL-204

The investigator may contact the sponsor's medical monitor/study physician for any other problem related to the rights, safety or well-being of the subject.

12.4.6 Reporting Procedures for Special Situations

12.4.6.1 Pregnancy

If a female subject becomes pregnant during the study dosing period or within 30 days from the discontinuation of dosing, the investigator is to report the information to the sponsor according to the timelines in [Appendix 12.4.5 Reporting Procedures for Serious Adverse Events using the SAE worksheet as a special situation and in the electronic data source.

The investigator will attempt to collect pregnancy information on any female partner of a male subject who becomes pregnant during the study dosing period or within 30 days from the discontinuation of dosing and report the information to the sponsor according to the timelines in [Appendix 12.4.5 Reporting Procedures for Serious Adverse Events] using the SAE worksheet as a special situation.

The expected date of delivery or expected date of the end of the pregnancy, last menstruation, estimated conception date, pregnancy result and neonatal data, etc., should be included in this information.

While pregnancy itself is not considered to be an AE or SAE, any pregnancy complication or termination (including elective termination) of a pregnancy is to be reported for a female subject as an AE in the electronic data source or SAE per [Appendix 12.4.5 Reporting Procedures for Serious Adverse Events]. For (S)AEs experienced by a female partner of a male subject, (S)AEs are to be reported via the SAE worksheet.

Additional information regarding the outcome of a pregnancy when also categorized as an SAE is mentioned below:

- "Spontaneous abortion" includes miscarriage, abortion and missed abortion
- Death of a newborn or infant within 1 month after birth is to be reported as an SAE regardless of its relationship with the IP
- If an infant die more than 1 month after the birth, it is to be reported if a relationship between the death and intrauterine exposure to the IP is judged as "possible" by the investigator
- Congenital anomaly (including anomaly in miscarried fetus)

Unless a congenital anomaly is identified prior to spontaneous abortion or miscarriage, the embryo or fetus should be assessed for congenital defects by visual examination or other means as appropriate. (S)AEs experienced by the newborn/infant should be reported via the pregnancy reporting form. Generally, follow up will be no longer than 6 to 8 weeks following the estimated delivery date.

12.4.6.2 Lack of Efficacy

Not applicable.

Sponsor: APGD ISN/Protocol: 178-CL-204

12.4.6.3 Medication Error, Overdose and "Off-label Use"

If a medication error (defined as an unintended failure in the treatment process that leads to, or has the potential to lead to, harm to the subject), overdose or "off-label use" (i.e., use outside of what is stated in the protocol) is suspected, refer to [Section 10.3 Major Protocol Deviations]. Any associated (S)AEs are to be reported in the electronic data source. If the AE meets the definition of an SAE, the SAE is also to be reported as described in [Appendix 12.4.5 Reporting Procedures for Serious Adverse Events] together with the details of the medication error, overdose and/or "off-label use."

In the event of suspected overdose, refer to the approved package insert, summary of product characteristics, or local product information supplied by the manufacturer for each IP.

12.4.6.4 Misuse/Abuse

Definition of misuse: Situations where the IP is/are intentionally and inappropriately used not in accordance with the intended use as defined in the protocol.

Definition of abuse: Persistent or sporadic, intentional excessive use of medicinal products which is accompanied by harmful physical or psychological effects.

If misuse or abuse of the IP is suspected, the investigator must forward the special situation worksheet to the sponsor by fax or email immediately (within 24 hours of awareness). Any associated (S)AEs are to be reported in the electronic data source. If the AE meets the definition of an SAE, the SAE is also to be reported as described in [Appendix 12.4.5 Reporting Procedures for Serious Adverse Events] together with details of the misuse or abuse of the IP.

12.4.6.5 Occupational Exposure

If occupational exposure (e.g., inadvertent exposure to the IP of study site personnel while preparing it for administration to the subject) to the IP occurs, the investigator must forward the special situation worksheet to the sponsor by fax or email immediately (within 24 hours of awareness). Any associated (S)AEs occurring to the individual associated with or resulting from the special situation are to be reported on the special situations worksheet.

12.4.6.6 (Suspicion of) Transmission of Infectious Agent

Not applicable.

12.4.6.7 Suspected Drug-drug Interaction

If a drug-drug interaction associated with the IP is suspected, the investigator must forward the special situation worksheet to the sponsor by fax or email immediately (within 24 hours of awareness). Any associated (S)AEs are to be reported in the electronic data source. If the AE meets the definition of an SAE, the SAE is also to be reported as described in [Appendix 12.4.5 Reporting Procedures for Serious Adverse Events] together with details of the suspected drug-drug interaction.

Sponsor: APGD ISN/Protocol: 178-CL-204

12.5 Liver Safety Monitoring and Assessment

The purpose of this appendix is to provide guidance for the monitoring of drug-induced liver injury during the course of the study. It should be noted that this section does not specify the EoS analyses of liver enzymes. The EoS liver enzymes analyses will be described in the SAP. Any subject enrolled in a study with active drug therapy and reveals an increase of serum aminotransferases (AT) to $> 3 \times \text{ULN}$ or bilirubin $> 2 \times \text{ULN}$ should undergo detailed testing for liver enzymes (including at least alkaline phosphatase [ALP], ALT, AST and TBL). Testing should be repeated within 72 hours of notification of the test results. For studies for which a central laboratory is used, alerts will be generated by the central laboratory regarding moderate and severe liver abnormality to inform the investigator and study team. Subjects should be asked if they have any symptoms suggestive of hepatobiliary dysfunction.

Definition of Liver Abnormalities

Confirmed abnormalities will be characterized as moderate and severe where ULN is as shown below.

Table 10 Moderate and Severe Liver Abnormalities

| | ALT or AST | | TBL |
|----------|------------|------|-----------|
| Moderate | > 3 × ULN | or | > 2 × ULN |
| Severe | > 3 × ULN | and† | > 2 × ULN |

ALT: alanine aminotransferase; AST: aspartate aminotransferase; TBL: total bilirubin; ULN: upper limit of normal

In addition, the subject should be considered to have severe hepatic abnormalities for any of the following:

- ALT or AST $> 8 \times ULN$
- ALT or AST $> 5 \times$ ULN for more than 2 weeks
- ALT or AST > $3 \times \text{ULN}$ and \dagger and TBL > $2 \times \text{ULN}$ or international normalized ratio (INR) > 1.5 (if INR testing is applicable/evaluated)
- ALT or AST $> 3 \times$ ULN with the appearance of fatigue, nausea, vomiting, right upper quadrant pain or tenderness, fever, rash and/or eosinophilia (> 5%)
- † Samples taken simultaneously or within a maximum of 24 hours.

The investigator may determine that abnormal liver function results, other than as described above, may qualify as moderate or severe abnormalities and require additional monitoring and follow-up.

Follow-up Procedures

Confirmed moderate and severe abnormalities in hepatic functions should be thoroughly characterized by obtaining appropriate expert consultations, detailed pertinent history, physical examination and clinical laboratory tests. The study site personnel are to complete the liver abnormality case report form (LA-CRF). Subjects with confirmed abnormal liver function testing should be followed as described below.

11 Feb 2021 Astellas Page 84 of 157

[†] Samples taken simultaneously or within maximum 24 hours.

Sponsor: APGD ISN/Protocol: 178-CL-204

Confirmed moderately abnormal liver function tests should be repeated 2 to 3 times weekly, and then weekly or less if abnormalities stabilize or the IP has been discontinued and the subject is asymptomatic.

Severe hepatic liver function abnormalities as defined above, in the absence of another etiology, may be considered an important medical event and may be reported as a SAE. The sponsor should be contacted and informed of all subjects for whom severe hepatic liver function abnormalities possibly attributable to IP are observed.

To further assess abnormal hepatic laboratory findings, the investigator is expected to:

- Obtain a more detailed history of symptoms and prior or concurrent diseases. Symptoms and new-onset diseases are to be recorded as "AEs" within the electronic data source. Illnesses and conditions such as hypotensive events and decompensated cardiac disease that may lead to secondary liver abnormalities should be noted. Nonalcoholic steatohepatitis is seen in obese hyperlipoproteinemic and/or diabetic subjects and may be associated with fluctuating AT levels. The investigator should ensure that the medical history form captures any illness that predates study enrollment that may be relevant in assessing hepatic function.
- Obtain a history of concomitant drug use (including nonprescription medication, complementary and alternative medications), alcohol use, recreational drug use and special diets. Medications are to be entered in the electronic data source. Information on alcohol, other substance use and diet should be entered on the LA-CRF or an appropriate document.
- Obtain a history of exposure to environmental chemical agents.
- Based on the subject's history, other testing may be appropriate including:
 - Acute viral hepatitis (A, B, C, D, E or other infectious agents)
 - Ultrasound or other imaging to assess biliary tract disease
 - Other clinical laboratory tests, including INR and direct bilirubin
- Consider gastroenterology or hepatology consultations.
- Submit results for any additional testing and possible etiology on the LA-CRF or an appropriate document.

Study Treatment Discontinuation

In the absence of an explanation for increased liver function tests, such as viral hepatitis, preexisting or acute liver disease, or exposure to other agents associated with liver injury, the subject may be discontinued from study treatment. The investigator may determine that it is not in the subject's best interest to continue study treatment. Discontinuation of study treatment should be considered if:

- ALT or AST $> 8 \times ULN$
- ALT or AST $> 5 \times ULN$ for more than 2 weeks
- ALT or AST > $3 \times \text{ULN}$ and † TBL > $2 \times \text{ULN}$ or INR > 1.5) (if INR testing is applicable/evaluated)

Sponsor: APGD ISN/Protocol: 178-CL-204 EudraCT number 2016-001767-37

- CONFIDENTIAL -

• ALT or AST $> 3 \times$ ULN with the appearance of fatigue, nausea, vomiting, right upper quadrant pain or tenderness, fever, rash and/or eosinophilia (> 5%)

† Samples taken simultaneously or within a maximum of 24 hours.

In addition, if close monitoring for a subject with moderate or severe hepatic laboratory tests is not possible, study treatment should be discontinued.

Hy's Law definition: Drug-induced jaundice caused by hepatocellular injury, without a significant obstructive component, has a high rate of bad outcomes, from 10% to 50% mortality (or transplant).

The 2 "requirements" for Hy's Law are:

- 1. Evidence that a drug can cause hepatocellular-type injury, generally shown by an increase in AT elevations > 3 × ULN ("2 × ULN elevations are too common in treated and untreated subjects to be discriminating").
- 2. Cases of increased TBL (at least 2 × ULN) with concurrent AT elevations at least 3 × ULN and no evidence of intra- or extra-hepatic bilirubin obstruction (elevated ALP) or Gilbert's syndrome [Temple, 2006].

FDA Guidance for Industry titled, "Drug-induced Liver Injury: Premarketing Clinical Evaluation" issued by the FDA on July 2009:

- 1. The drug causes hepatocellular injury, generally shown by a higher incidence of 3-fold or greater elevations above the ULN of ALT or AST than the (nonhepatotoxic) control drug or placebo.
- 2. Among subjects showing such AT elevations, often with ATs much greater than $3 \times \text{ULN}$, 1 or more also show elevation of serum TBL to $> 2 \times \text{ULN}$, without initial findings of cholestasis (elevated serum ALP).
- 3. No other reason can be found to explain the combination of increased AT and TBL, such as viral hepatitis A, B or C; preexisting or acute liver disease; or another drug capable of causing the observed injury.

References

Temple R. Hy's Law: Predicting Serious Hepatotoxicity. Pharmacoepidemiol Drug Saf. 2006; 15:241-3.

ISN/Protocol: 178-CL-204

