6.6 Dose Modification

At visit 5/week 4 (i.e., after 4 weeks on PED25), dose up-titration to PED50 will be performed unless the investigator determines that the subject is adequately treated for OAB at the PED25 dose or if there are safety concerns identified and considered associated with the use of PED25.

At any time, down-titration from PED50 to PED25 can be performed if there is an AE possibly related to the drug that is considered bothersome by the subject or that leads to medical intervention (e.g., initiation of medication therapy to treat the AE). Of note, PED25 is the lowest dose to be used in this study.

Criteria for discontinuation of individual subject(s) from study treatment are listed in [Section 8.1 Discontinuation of Individual Subject(s) from Study Treatment(s)].

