7.2.2 Laboratory Assessments

Blood samples for hematology and biochemistry and urine samples for urinalysis will be collected as indicated in the Schedule of Assessments [Table 1]. All clinical laboratory assessments will be performed at a central laboratory except for urinalysis dipsticks which will be conducted locally to support study eligibility or AEs. A urine pregnancy test in female subjects of childbearing potential will be performed at all on-site visits. A topical anesthetic cream or plaster must be offered at the point of venipuncture to minimize distress of the subject. For sampling the arm opposite to the arm used for blood pressure measurements should be used (i.e., preferably the left arm). Blood sampling should occur after vital signs and ECG measurements.

Sample collection, handling and storage will be described in a laboratory manual. All clinical laboratory test results, including ULNs used in exclusion and discontinuation criteria, will be compared to age appropriate norms.

Sponsor: APGD EudraCT number 2016-001767-37 - CONFIDENTIAL -

ponsor: APGD ISN/Protocol: 178-CL-204

Scheduled blood sampling will only be performed at screening (visit 1), week 4 (visit 5) and EoT (visit 7) to keep the burden to subjects at a minimum. Additional hematology, biochemistry and urinalysis (urinalysis dipstick) tests will be performed at visit 3/week 0 (baseline) and visit 8/week 14 (EoS) only if an AE related to hematology, biochemistry or urinalysis parameters occurred since the previous visit or at the discretion of the investigator. If any of the clinical laboratory tests results are outside the normal range at any scheduled time point during the study, the investigator may decide to repeat the test(s) on new samples. The clinical relevance of the abnormal results will be documented. Clinically relevant changes will be recorded as AEs (see [Section 7.3 Adverse Events and Other Safety Aspects]).

Refer to the Alternate Schedule of Assessments [Table 12] for acceptable alternate methods to assess safety and efficacy parameters in the event the study is interrupted due to a crisis (e.g., natural disaster, pandemic).

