8 DISCONTINUATION

8.1 Discontinuation of Individual Subject(s) From Study Treatment(s)

A discontinuation from treatment is defined as a subject who is randomized and for whom study treatment is permanently discontinued for any reason.

The subject is free to withdraw from the study treatment and/or study for any reason and at any time without giving reason for doing so and without penalty or prejudice. The investigator is also free to discontinue the participant from study treatment or to terminate a subject's involvement in the study at any time if the subject's clinical condition warrants it.

The reason for discontinuation from study treatment must be documented in the subject's medical records.

[‡] Volume does not take any unscheduled visits or repeat tests into account (e.g., follow up of adverse events).

Sponsor: APGD ISN/Protocol: 178-CL-204

A subject must discontinue study treatment for any of the following reasons:

- Subject requests to stop treatment.
- Any clinical AEs, laboratory abnormality or intercurrent illness, in the opinion of the investigator, indicates continued treatment is not in the best interest of the subject.
- If signs or symptoms of hypersensitivity to mirabegron are observed (e.g., anaphylactic reaction, erythema multiforme or exfoliative dermatitis).
- ALT or AST $> 8 \times ULN$.
- ALT or AST $> 5 \times ULN$ for more than 2 weeks.
- ALT or AST > $3 \times \text{ULN}$ and TBL > $2 \times \text{ULN}$ or international normalized ratio (INR) > 1.5 (if INR testing is applicable/evaluated).
- ALT or AST $> 3 \times$ ULN with the appearance of fatigue, nausea, vomiting, right upper quadrant pain or tenderness, fever, rash and/or eosinophilia (> 5%).
- Female subject becomes pregnant.
- Prolongation of QT > QTcF > 440 msec and/or QT interval prolongation > 30 msec versus baseline.
- Subject with (systolic blood pressure ≥ 160 mm Hg or diastolic blood pressure ≥ 100 mmHg.

If a subject discontinues treatment prematurely, the subject will be encouraged to complete all scheduled visits to record all available information.

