10.3 Major Protocol Deviations

A protocol deviation is generally an unplanned excursion from the protocol that is not implemented or intended as a systematic change. All deviations from the protocol are to be recorded. A protocol waiver is a documented prospective approval of a request from an investigator to deviate from the protocol. Protocol waivers are strictly prohibited.

The investigator is responsible for ensuring the study is conducted in accordance with the procedures and evaluations described in this protocol and must protect the rights, safety and well-being of subjects. The investigator should not implement any deviation from, or changes of, the protocol, unless it is necessary to eliminate an immediate hazard to subjects.

A major protocol deviation is 1 that may potentially impact the completeness, accuracy or reliability of data contributing to the primary endpoint or affect the rights, safety or well-being of a subject. Major protocol deviations will have additional reporting requirements.

When a major deviation from the protocol is identified for an individual subject, the investigator or designee must ensure the sponsor is notified. The sponsor will follow up with

- CONFIDENTIAL -

the investigator, as applicable, to assess the deviation and the possible impact to the safety and/or efficacy of the subject to determine subject continuation in the study.

ISN/Protocol: 178-CL-204

The major protocol deviation criteria that will be summarized at the EoS are as follows:

- PD1 Entered into the study even though the subject did not satisfy entry criteria
- PD2 Developed withdrawal criteria during the study and was not withdrawn
- PD3 Received wrong treatment or incorrect dose
- PD4 Received excluded concomitant treatment

The investigator will also assure that deviations meeting IRB/IEC and appropriate regulatory authorities' criteria are documented and communicated appropriately. All documentation and communications to the IRB/IEC and appropriate regulatory authorities will be provided to the sponsor and maintained within the Trial Master File.

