12.4.1.2 Potential Cases of Drug-induced Liver Injury

Refer to [Appendix 12.5 Liver Safety Monitoring and Assessment] for detailed instructions on drug induced liver injury. Abnormal values in AST and/or ALT concurrent or with abnormal elevations in TBL that meet the criteria outlined in [Appendix 12.5 Liver Safety Monitoring and Assessment], in the absence of other causes of liver injury, are considered potential cases of drug-induced liver injury (potential Hy's Law cases) and are always to be considered important medical events and reported per [Appendix 12.4.5 Reporting Procedures for Serious Adverse Events].

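### Appendix 12.5 leaves stopping to the investigator's judgement at the same four liver criteria where Section 8.1 and the synopsis make it mandatory

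*Protocol*

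**What the plan says.** Protocol Section 8.1 opens its list with "A subject must discontinue study treatment for any of the following reasons". The synopsis, under Treatment Discontinuation Criteria, opens the same way. Both lists contain four liver criteria:

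1. ALT or AST above 8 × ULN.
2. ALT or AST above 5 × ULN for more than 2 weeks.
3. ALT or AST above 3 × ULN, with total bilirubin above 2 × ULN or INR above 1.5.
4. ALT or AST above 3 × ULN with listed symptoms or eosinophilia.

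Neither place makes the stop depend on whether another cause has been found.

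Appendix 12.5 has its own part on study treatment discontinuation. It begins by saying that, where no explanation such as viral hepatitis has been found, "the subject may be discontinued from study treatment". It then writes "Discontinuation of study treatment should be considered if" and gives the same four criteria. A footnote there asks that the paired samples in criterion 3 be simultaneous or at most 24 hours apart. Section 8.1 and the synopsis carry no such footnote.

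On which text governs, Section 6.6 says "Criteria for discontinuation of individual subject(s) from study treatment are listed in" Section 8.1. Section 12.4.1.2 refers the reader to Appendix 12.5 "for detailed instructions on drug induced liver injury". Appendix 12.5 does not mention 8.1, and no statement of precedence appears.

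**The concern.** Two parts of the current protocol give different instructions for the same laboratory result. A central-laboratory liver alert is most naturally handled from Appendix 12.5, because that is where the protocol sends investigators for drug-induced liver injury. An investigator who reads only that appendix may consider stopping, decide against it, and believe the protocol has been followed. Under 8.1 the same child had to stop.

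The gap is widest when another cause is suspected. With ALT above 8 × ULN and, say, a possible viral hepatitis, 8.1 still requires a stop, while the 12.5 lead-in does not reach the case and its list asks only for consideration.

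What is at stake is a child's continued exposure to study drug after a liver stopping threshold, and a possible major deviation under Section 10.3 ("PD2 Developed withdrawal criteria during the study and was not withdrawn"). The planned efficacy analysis is not touched.

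**Working it through.** There is no planned figure to reproduce. The check is a comparison of texts, followed by a bound on the exposure.

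**Comparison**

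| Liver criterion | Section 8.1 and synopsis | Appendix 12.5 |
|---|---|---|
| 1. > 8 × ULN | must stop | consider stopping |
| 2. > 5 × ULN for > 2 weeks | must stop | consider stopping |
| 3. > 3 × ULN with bilirubin > 2 × ULN or INR > 1.5 | must stop | consider stopping (24-hour footnote) |
| 4. > 3 × ULN with symptoms or eosinophilia | must stop | consider stopping |
| Another cause identified | no exception | lead-in covers unexplained elevations only |

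The thresholds match on 4 of 4 criteria and the obligation differs on 4 of 4.

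**Where the discretion can matter**

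Section 7.2.2 schedules blood sampling at screening, week 4 and week 12 (EoT) only. The screening draw precedes dosing, and Section 4.1 stops the drug at week 12. That leaves one scheduled draw, week 4, plus any repeat or unscheduled tests.

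**Remaining dosing after the week 4 draw**

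Inputs from the Schedule of Assessments: week 4 is day 28 ± 3 and week 12 is day 84 ± 3.

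- Nominal: 84 − 28 = 56 days, which is 56/84 = 67% of the treatment period.
- Longest with windows: (84 + 3) − (28 − 3) = 87 − 25 = 62 days.
- Shortest with windows: (84 − 3) − (28 + 3) = 81 − 31 = 50 days.

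These figures apply to criteria 1, 3 and 4. Criterion 2 needs more than 14 days above 5 × ULN. If the elevation is first seen at week 4, the criterion is met after day 28 + 14 = 42:

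- Nominal: under 84 − 42 = 42 days.
- Longest with windows: under 62 − 14 = 48 days.

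Criterion 2 can be established only through repeat or unscheduled tests, because the scheduled draws at weeks 4 and 12 are nominally 56 days apart. INR is not in the scheduled panel (Appendix 12.7), so the INR part of criterion 3 also needs an extra test.

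All of these are upper bounds. They count from the day of the draw, before the result is known, and assume that dosing then runs uninterrupted to week 12.

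**The case against.** The best defence is that both texts can be obeyed at once: a site that stops under 8.1 breaches nothing in 12.5. Appendix 12.5 describes itself as guidance on monitoring and reads like generic text. Section 6.6 names 8.1 as the home of the discontinuation criteria, and the mandatory rule is stated twice. This helps to identify the operative rule and supports the direction of the fix. It does not remove the conflict, because a site can also follow 12.5 faithfully and breach 8.1.

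A second defence stands in part. Appendix 12.5 provides for central-laboratory alerts on moderate and severe liver abnormalities to both the investigator and the study team, a repeat test within 72 hours of notification, and expert work-up. A missed stop is therefore less likely to go unnoticed, and uninterrupted dosing to week 12 is a worst case.

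Some stronger readings are tempting and are not supported:

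- A reader might infer from "if close monitoring for a subject with moderate or severe hepatic laboratory tests is not possible, study treatment should be discontinued" that dosing may continue in severe cases when monitoring is possible. That does not follow. The sentence is introduced as an additional ground for stopping and is silent on what happens when monitoring is possible.
- A reader might treat PD2 as automatic. PD2 speaks of withdrawal criteria, while Section 8.2 keeps subjects who stop treatment in the study. The protocol never says that the 8.1 treatment stops are PD2 criteria. Such a case could be recorded as PD2; that it would be is not certain.
- A reader might also see a conflict on SAE reporting, because 12.5 says severe abnormalities may be reported and 12.4.1.2 says potential Hy's Law cases always are. The latter is a specific rule beside a general one, and Section 7.3.6 already requires 24-hour reporting of hepatotoxicity. That is not part of this point.

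**Conclusion.** The protocol contradicts itself on a safety stopping rule: four of four liver criteria are mandatory in Section 8.1 and the synopsis and discretionary in Appendix 12.5. It should be corrected.

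The consequence is limited. It arises at one scheduled draw and at any extra tests. Applying 56 days to all four criteria would overstate it, since criterion 2 leaves less time. The documents give no expected number of cases, so none is claimed.

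That the mandatory version is the intended one is an inference about the sponsor's intent. It rests on the two mandatory statements and the Section 6.6 pointer, and it is the more protective reading for children. The finding applies to protocol version 2.0, the version supplied.

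**What to change.** Make two changes in Appendix 12.5, in the part on study treatment discontinuation:

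1. Replace the sentence "Discontinuation of study treatment should be considered if" and the list beneath it with: *Study treatment must be discontinued if any liver criterion in Section 8.1 is met, whether or not another cause is identified.*
2. Limit the permissive lead-in to liver abnormalities that meet none of the Section 8.1 criteria. Without this, the discretion survives the first change.

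Pointing to 8.1 is better than putting a mandatory verb over the existing list, because that list carries the 24-hour footnote. A child meeting criterion 3 on samples more than 24 hours apart would have to stop under 8.1 but would still fall under the permissive lead-in of 12.5. If the sponsor wants the 24-hour condition to apply to the mandatory stop, it should be added to 8.1 and the synopsis in the same edit.

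The close-monitoring sentence can stay as an additional reason to stop. The cost is protocol wording in one appendix, plus a footnote in two other places if the sponsor chooses it. Visits, assessments, data collection and analyses are unchanged.
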